3.3.3 Ancillary Safety Outcome Measures

We will report all adverse and serious adverse events for both study groups as described in the investigators brochure guide.⁴ In addition, we will run an immunoglobulin panel in the switching group as well.

3.4 Safety Plan

Patients will be evaluated at each study visit for the duration of their participation in the study (see Table 1 under section 4.5 for schedule of events conducted on the switching group; comparator group is standard of care). Patients will be interviewed by the study coordinator at each visit to determine additional safety issues. See Section 5 (Assessment of Safety) for complete details of the safety evaluation for this study.

3.5 Compliance with Laws and Regulations

This study will be conducted in accordance with current U.S. Food and Drug Administration (FDA) Good Clinical Practices (GCPs), and local ethical and legal requirements. An investigator held IND has been granted (IND number 132705).

4. MATERIALS AND METHODS

4.1 Subjects

We plan to enroll 100 patients in the switching group and between 100 and 200 patients in the comparator group (to study 200 infusions) for a total of up to 200-300 patients which would provide adequate power (90%) for the study. To account for screen failures and withdrawals, we are seeking to enroll an additional 50 patients for a total of 250-350 patients. Patients are not confined to only one of the 2 groups. For example, data may be collected from a patient as part of the rituximab arm and then at a later point the patient decides to switch to ocrelizumab. This patient could then be consented into the switching group. Enrollment will occur over a 3-month period at RMMSC.. Dropouts in the switching group that occur prior to the 6 month infusion will be replaced. All patients will be included in the analyses (Intent to Treat Analysis).

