4.9.4 Safety Analysis

The default analysis will be available case for all eligible participants on an intent to treat basis. Alpha = 0.05 for all tests. As in the OPERA I and II randomized clinical trials, the primary and secondary end points will be descriptively presented. Frequencies and percentages for the severity of IRR grades (Grades 0-5) will be presented for both study groups following each infusion time point and overall between groups. 95% confidence intervals for the proportions will be calculated. Differences in the distribution of IRR severity grades between independent samples (i.e. comparison between groups at a common time point) will be tested with the chi-square or Fisher's exact association test, and additionally with ordinal or multinomial logistic regression. If sample sizes are small among some levels of IRR severity grades, they may be collapsed or dichotomized (i.e. Grade 3 or higher, any reaction or no reaction, severe reaction or none as examples) and methods described for binary outcomes under secondary endpoints will be utilized. Dichotomization may be used to make analysis and presentation of results more manageable as well.

The primary endpoint will be the proportion of whether any IRR occurred (yes or no) per infusion cycle per patient in each study group. The secondary endpoints include the proportion per infusion per patient of severe infusion reaction (grade 3 or greater), the proportion of infusion reactions and severe infusion reaction per patient across all infusions, the proportion patients with anti-drug antibodies, and the proportion of patients with depleted B cells. The primary outcome, binary occurrence of IRR per infusion per patient, could be analyzed with logistic or relative risk models, with GEE (generalized estimating equations) and/or GLMM

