(generalized linear mixed models) methods to incorporate correlation on repeated infusions on a patient. The same method will apply to other longitudinal binary outcomes. Poisson or negative binomial models with exposure terms could calculate rates of IRR per infusion per patient as a counting process. Similar methods will be used to compare IRR rates between the switching group and OPERA I and II phase 3 clinical trials. The total number of IRRs experienced in each patient, will be analyzed with Poisson or negative binomial models. Paired T tests will be used to assess differences in specific cytokine markers between pre and post infusion at each infusion cycle. Patient reported outcomes will also be reported descriptively. Frequencies and proportions will be reported for adverse and serious events and loss to follow up

As contingency methodology, exact tests and confidence intervals for measures of association between categorical variables can be utilized when necessary, if the sample sizes for some of the cells are small. Transforms or rank based methods, such as Wilcoxon sign rank, can be used in place of the T-test if deviation for normality is severe. Otherwise the T-test is a robust test of mean differences for medium to large sample sizes. If matching leads to good balance between the treatment groups on the demographic and disease variables, including age, MS disease duration, and baseline PDDS score, then confounding will not be an issue and the proposed unadjusted tests should be adequate. Alternatively, if the demographic and disease variables are not balanced, then regression or propensity score methods will be used to adjust for potential confounding. Sensitivity analysis comparing unadjusted and adjusted results will be used to determine the extent of the confounding effect. Adjustment for covariates can sometimes improve the precision of the estimated treatment difference by reducing random noise in the outcome.

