4.9.6 Determination of Sample Size

The sample size will be a convenience sample. It is anticipated a minimum of 100 patients will qualify for each cohort (200 total) resulting in studying 300 infusions with ocrelizumab and 200 infusions with rituximab. This is an observational study not designed to demonstrate superiority of ocrelizumab over rituximab in efficacy but instead indicate the magnitude of the relative tolerability and immunogenicity. The primary endpoint is the difference in the percentage of IRRs between the two study groups. In addition, both study groups will include treatment experienced patients on rituximab who have experienced a minimum of two infusions and either continue to stay on rituximab or switch to ocrelizumab.

To estimate study power with the proposed sample size of 100 infusions in each group, we conducted a chart review of 50 patients at the Rocky Mountain MS Center who are currently taking rituximab and examined their IRRs using the proposed IRR grading scale (see section 3.3.1) from Grade 0-5. The number and severity of IRRs were captured following their third rituximab infusion. The highest grade of an IRR that occurred during the infusion was recorded. Our pilot data revealed that following the third rituximab infusion, 14.3% of patients had an IRR of which 85.71% were Grade 0, 12.24% were grade 2 and 2.05% were Grade 3. Hauser et al., found that following the second infusion of rituximab in patients, the majority of whom (60%) were not taking a DMT for 6 months prior to initiating rituximab only 20.3% experienced in an IRR.³

Using IRR estimates from our pilot data and establishing a clinically meaningful difference of 20% increase in IRRs, we conducted the following power analysis for a sample of 95 patients (assuming a 5% attrition rate after recruiting 100 patients in each study group). An IRR proportion for ocrelizumab users at 34.3% compared with 14.3% for rituximab (obtained from our pilot data) for a two sided (alpha = 0.05) two sample proportion test for the null hypothesis of no difference between rituximab and ocrelizumab in proportion of IRRs would result in 90% power for 95 patients per group.

In response to the FDA IND letter, “the power analysis in Section 4.9.6 of the protocol appears to compare the infusion-related reaction (IRR) rate at the third rituximab infusion (14.3%) to that of the first infusion of OCR (34.3%). Because

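### One patient may be in both groups, yet the between-group severity tests assume independent samples and no rule keeps one identifier across both enrolments

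*Combined protocol and SAP*

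**What the plan says.** Section 4.1 states "Patients are not confined to only one of the 2 groups". Its example is a patient who supplies rituximab data and later decides to change drug: "This patient could then be consented into the switching group". It gives no cap on such patients, no identifier rule and no analysis rule.

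Section 4.9.4 describes the severity analysis as "Differences in the distribution of IRR severity grades between independent samples (i.e. comparison between groups at a common time point", tested by chi-square or Fisher and also by ordinal or multinomial logistic regression with no clustering stated. For the primary endpoint (any IRR, per infusion per patient) the same section says that logistic or relative risk models could be used with GEE and/or GLMM "to incorporate correlation on repeated infusions on a patient", and extends this to other longitudinal binary outcomes.

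The power calculation in section 4.9.6 rests on a "two sided (alpha = 0.05) two sample proportion test", which also supposes different people in each group.

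Section 3.1 calls the design both between-group and within-group. The only within-patient IRR comparison defined in section 3.3.1 is ocrelizumab day 1 against day 15 and month 6.

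**The concern.** If the same person supplies infusions to both groups, the two group estimates are positively correlated, and a test for independent samples uses the wrong variance for their difference. A person consented twice may also carry two study numbers. A model clustered on study number would then treat that person as two people, and the patient total would be overstated.

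Overlap is plausible. Section 1 says that rituximab users at the centre are being counselled about switching. Section 4.2 offers switching to suitable rituximab-arm patients. Section 3.1 allows comparator infusions to be collected retrospectively from August 2016. Matching in section 4.2 is on gender and age within two years, so nothing written stops a patient being matched to himself or herself.

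The direction matters in a tolerability study. Where the variance is overstated, intervals are too wide, and a real increase in IRRs after switching is harder to see. In addition, where people overlap, their own rituximab and ocrelizumab infusions allow a comparison free of stable patient differences, and the plan does not define one.

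**Working it through.** **1. The plan's own figure.** Inputs from section 4.9.6: "An IRR proportion for ocrelizumab users at 34.3% compared with 14.3% for rituximab", 95 per group ("assuming a 5% attrition rate after recruiting 100 patients in each study group"), two-sided alpha 0.05.

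- Pooled proportion 0.243, so the null SE is √(2 × 0.243 × 0.757 / 95) = 0.0622.
- Unpooled SE is √[(0.143 × 0.857 + 0.343 × 0.657) / 95] = 0.0605.
- Power = Φ[(0.20 − 1.96 × 0.0622) / 0.0605] = Φ(1.29) = 0.90.

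The claim "would result in 90% power for 95 patients per group" reproduces under independence.

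**2. Assumptions.** The documents give neither f nor r. I take f = 0.25 to 0.5 of each 100-patient group and r = 0.2 to 0.4, with f = r = 0.1 as a mild case. Let n = 100 and let s² be a common variance per infusion. Section 4.9.6 expects 300 ocrelizumab infusions (3 per switcher) and 200 rituximab infusions. Section 4.1 allows 100 to 200 comparators, hence 100 × 2 or 200 × 1.

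**3. Formulas for the variance of the difference, in units of s²/n.**

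- *Independent-samples test at a common time point, equal groups.* Assumed 2; true 2(1 − fr); ratio 1/(1 − fr).
- *GEE with a separate identifier per group, 100 × 2.* Assumed (1 + 2r)/3 + (1 + r)/2; true value is that minus 2fr.
- *GEE with a separate identifier per group, 200 × 1.* Assumed (1 + 2r)/3 + 1/2; true value is that minus fr (100f people overlap).
- *Chi-square pooled over infusions, 100 × 2.* Assumed 1/3 + 1/2 = 0.833; true value as in the 100 × 2 line above.

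**4. Results: assumed variance divided by true variance.**

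| f | r | Common time point | Separate IDs, 100 × 2 | Separate IDs, 200 × 1 | Pooled chi-square, 100 × 2 |
|---|---|---|---|---|---|
| 0.10 | 0.1 | 1.01 | 0.950/0.930 = 1.02 | 0.900/0.890 = 1.01 | 0.833/0.930 = 0.90 |
| 0.25 | 0.2 | 1.05 | 1.067/0.967 = 1.10 | 0.967/0.917 = 1.05 | 0.833/0.967 = 0.86 |
| 0.25 | 0.4 | 1.11 | 1.300/1.100 = 1.18 | 1.100/1.000 = 1.10 | 0.833/1.100 = 0.76 |
| 0.50 | 0.2 | 1.11 | 1.067/0.867 = 1.23 | 0.967/0.867 = 1.12 | 0.833/0.867 = 0.96 |
| 0.50 | 0.4 | 1.25 | 1.300/0.900 = 1.44 | 1.100/0.900 = 1.22 | 0.833/0.900 = 0.93 |

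The first three methods err on the conservative side. At a common time point the SE is too large by √1.053 − 1 = 2.6% up to √1.25 − 1 = 12%.

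The pooled chi-square errs the other way. Its variance is 14% too small at f = 0.25, r = 0.2 and 7% too small at f = 0.5, r = 0.4; the two crossed settings give 24% and 4%. The cause is the ignored repeat infusions, and overlap offsets part of it. The true value is 0.833 + r(7/6 − 2f), so the sign changes only when f exceeds 7/12 = 0.58, whatever r is.

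**5. Effect on the plan's test, one infusion per patient, 95 per group.** The true variance is [p₁q₁ + p₂q₂ − 2fr√(p₁q₁p₂q₂)]/95. At f = 0.25, r = 0.2 the true SE is 0.0591 against 0.0605 assumed, and the actual alpha is 0.044. At f = 0.5, r = 0.3 the true SE is 0.0560 and alpha is 0.034. Power of the uncorrected test is 0.907 and 0.918, so it stays above 90%. With the correct variance, power is 0.923 and 0.946, against 0.911 for the same unpooled formula without overlap.

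**6. Simulation under the null** (600 runs per setting, 14.3% in both groups, 100 × 3 and 100 × 2 infusions, latent within-patient correlation 0.5, Monte Carlo SE about 0.009).

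| f | GEE, one ID | GEE, separate IDs | Pooled chi-square |
|---|---|---|---|
| 0 | 0.048 | 0.048 | 0.097 |
| 0.25 | 0.055 | 0.043 | 0.075 |
| 0.5 | 0.067 | 0.038 | 0.067 |
| 1 | 0.055 | 0.008 | 0.023 |

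One identifier keeps alpha within about two Monte Carlo SEs of 0.05 at every overlap. Separate identifiers become increasingly conservative.

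**7. Head count.** At f = 0.5, 100 + 100 enrolments are 150 people, of whom 50 (33%) are in both groups.

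**The case against.** The strongest reply is that the plan already names the remedy. Section 4.9.4 proposes GEE or GLMM with the patient as the unit of correlation, and someone with infusions of both drugs is, on a plain reading, one patient. A reader might infer that the standard errors are wrong throughout; the documents do not support that, and the primary endpoint is sound if the patient is the cluster across both groups. What remains is that the method is only offered as a possibility, one identifier is never required, and the severity comparison is expressly assigned to independent-samples tests.

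Second, overlap may be small: section 4.1.2 asks that comparators will continue on rituximab at the centre. This is fair, and the mild case shows little effect. But the same section accepts retrospective rituximab data, and section 4.1 sets no limit.

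Third, the tests in section 4.9.2 also assume independent groups. They compare baseline variables and discontinuations, so they do not affect the error of the IRR difference.

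Fourth, it is tempting to say that the within-patient drug contrast is thrown away. It is undefined rather than discarded, because a model clustered on person uses that information. It would also be limited: in the example in section 4.1 rituximab comes first, so drug is tied to time order, and section 4.2 concedes that IRRs are not collected in the same way in the two groups.

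**Conclusion.** The point holds for the between-group severity comparison, and for the primary endpoint only if identifiers are not linked. There is no single direction of error. Over the assumed range, the common-time-point test and GEE with separate identifiers are conservative, while the pooled chi-square is anti-conservative for a different reason, the repeat infusions.

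A reader might infer that overlap inflates type I error or invalidates the power statement. It does neither: under positive correlation overlap alone makes an independent-samples test conservative, and the plan's 90% stands. All sizes rest on assumed f and r and on a common variance. With 200 comparators, or with overlap near 10%, they shrink to the lower figures shown. The matter is modest in size but inexpensive to settle before analysis.

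**What to change.** - Give each person one identifier across both groups, and say so in section 4.1 and section 4.9.4.
- Make GEE or GLMM clustered on person the firm method for the primary endpoint, in place of the optional wording.
- Where people overlap, replace chi-square and Fisher by person-clustered models for between-group IRR and severity comparisons.
- State in section 4.2 that a patient may not be matched to himself or herself.
- Report the number of people in both groups and the number of unique people.
- Add a within-person rituximab versus ocrelizumab comparison as a sensitivity analysis, with its limits stated: time order and the different IRR collection methods.

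The cost is SAP wording and a link between study numbers. No new data are needed.

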4.1.1 Subject Selection

All subjects will be MS patients receiving care at the RMMSC at the University of Colorado Hospital

4.1.2 Inclusion Criteria

Switching group:

- Current active patient of RMMSC
- 18-65 years
- Diagnosis of relapsing forms of MS
- Completed **≥ two doses** of rituximab with the last dose having been administered:
 - a) within 12 months of screening
 - and
 - b) at least 6 months prior to first planned infusion of study drug
- Are receiving their current infusions of rituximab at the University of Colorado Outpatient Infusion Center
- Have discussed the possibility of switching to ocrelizumab with their MS provider
- Screened for Hepatitis B and C and TB within 2 years of first dose of ocrelizumab
- A negative serum pregnancy test must be available for premenopausal women and for women <12 months after the onset of menopause, unless they have undergone surgical sterilization.
- Women of childbearing potential must agree to use a “highly effective”, hormonal form of contraception or two “effective” forms of non-hormonal contraception. Contraception must continue for the duration of study treatment and for at least three months after the last dose of study treatment
- Are able to complete patient reported outcomes developed as English written scales.
- Must be able and willing to give meaningful, written informed consent prior to participation in the trial, in accordance with local regulatory requirements

Comparator group:

- Current active patient of RMMSC

- 18-65 years
- Diagnosis of relapsing forms of MS
- Completed \geq **two doses** of rituximab with the last dose having been administered within 12 months of screening as standard of care
- Are receiving their current infusions of rituximab as standard of care at the University of Colorado Outpatient Infusion Center and will continue to do so
- Are willing to be followed for subsequent rituximab infusions during the study period as standard of care, and/or allow retrospective data collection on previous rituximab infusions
- Must be able and willing to give meaningful, written informed consent prior to participation in the trial, in accordance with local regulatory requirements

4.1.3 Exclusion Criteria

Both groups:

- Pregnant or lactating women
- Hypersensitivity to trial medications
- Hepatic Dysfunction (liver enzymes are 5 times greater than normal)
- History of Congestive Heart Failure
- Any history of a positive blood assay for Hepatitis B or C
- Any history of TB or a positive Quantiferon Gold Assay
- Concurrent use of immunosuppressant medications
- Any history of immunodeficiency or other medical condition increasing risk of anti-CD 20 therapy.
- Serious infection at the time of a scheduled study infusion.
- Any medical, psychiatric or other condition that could result in the patient not being able to give fully informed consent, or to comply with the protocol requirements as determined by the investigator

4.2 Method of Treatment Assignment

The study will not be a randomized trial. Patients will not be assigned to the switching group, but rather will be enrolled after a clinical decision has been made with their provider about whether they will continue on rituximab or switch

to ocrelizumab. The following steps will be taken to minimize potential biases in sample selection.

First, in an effort to impose some degree of similarity between the treatment groups, control patients will be matched, either 1:1 or 2:1 depending on the number of control patients, with switching patients on gender and age (+/- 2 years) at recruitment. The demographic information on switching patients will be scanned to find matches for the patients in the non-switching group.

Furthermore, screening of additional patients beyond the 200 required for enrollment in the non-switching group will be also conducted to ensure the best possible matches. Second, baseline statistics will be monitored as patients enter the study, and selection of patients may be modified in order to maintain relative balance between treatment groups (if necessary using measures of disease severity other than age and gender) if we are able to overenroll the number of non-switchers. Third, demographic variables and measures of baseline disease severity, including age, gender, MS disease duration, type of MS at baseline (first infusion in both study groups), along with discontinuations, will be recorded and compared between treatment groups.

All available observations will be used. For continuous variables (age, MS disease duration), by treatment group means, standard deviations, medians, and ranges will be recorded, and differences among treatment groups will be tested for with either with T-test/ANOVA methods or Wilcoxon/Kruskal Wallis tests. For categorical variables (gender, type of MS, disability, discontinuations), frequencies and proportions will be presented, and differences among treatment groups will be tested for using chi-square/Fisher's exact test. Fourth, following these measures, if treatment confounding is found to still be an issue, regression or propensity score methods, with covariates such as age, MS disease duration, and baseline EDSS score will be used post hoc to minimize confounding.

Potential study patients will be identified from RMMSC electronic medical records (EPIC) using the study inclusion and exclusion criteria. Patients will be recruited by the study coordinator through the University of Colorado's Outpatient Infusion Center. Potential patients are already being identified through their MS providers at RMMSC with whom discussions about the possibility of switching to ocrelizumab are currently underway. Study participants who complete the observation phase of the study will be offered the ability to continue to receive ocrelizumab infusions provided for free by Genentech until ocrelizumab is approved and available to them through their health insurance plan. Once ocrelizumab is available by prescription they will receive priority for assistance through the Genentech/Roche Patient Assistance Program for Ocrelizumab for out of pocket expenses. Ocrelizumab will be provided through priority placement in Genentech's patient assistance program for those patients who are not able to receive insurance coverage for it.

MS patients included in this study will have made a decision with their provider to either stay on rituximab or to switch to ocrelizumab outside of this study. The decision to switch to ocrelizumab or to stay on rituximab will be made as part of

the clinical treatment process between the patient and his/her provider based on his/her disease severity and suitability for treatment among other factors. Therefore, patients are not randomized into either treatment arm. For the group that stays on rituximab, participation in this study is purely observational. For those patients in the rituximab arm who are deemed to be appropriate candidates for switching to ocrelizumab, the option to do so will be provided as standard of care under priority access and/or patient assistance programs (contingent on their individual health insurance status).

It is important to note that because the incidence of IRRs for infusions prior to enrollment are not collected prospectively for those continuing treatment with rituximab and because adverse events including IRRs will not be collected using the same methods for each treatment group following enrollment, interpretation of any difference in the incidence of these events will be limited.

